##### Emergency Unblinding Procedures:

Examples of emergencies include 1) a life-threatening unexpected adverse event that is at least possibly related to the investigational agent and for which unblinding would influence treatment decisions; or 2) medication error, such as accidental overdose. Expected adverse events are listed in the “Toxicities” section below.

Contact the Alliance Executive Officer on call by calling [REDACTED], pressing 1 to speak with an operator, and then asking for [name] to return the call.

The institution must provide the following information to the Alliance Executive Officer:

- Alliance study ID (i.e., “A#####”)
- Alliance patient ID number (e.g., “999999”)
- Patient initials (e.g., “L,FM”)
- Institution name
- Name and telephone number of treating physician
- Name and contact information of person requesting the unblinding procedure
- Name and contact information of person to inform of treatment assignment
- Reason for emergency unblinding

Please remember that emergency unblinding request may be authorized only by an Alliance Executive Officer, and emergency unblinding applies only if unblinding would influence management of the medical situation.

After the Executive Officer deems unblinding is warranted, the treatment assignment will be provided to the contact person at the treating site.

### **7.2.2 Protocol-specified unblinding**

Trial participants may be unblinded upon study completion. Contact the Alliance Registration Office at [REDACTED] during regular business hours. Upon confirmation by the Primary Statistician (or designee) that all study completion requirements have been met, the treatment assignment may be unblinded. No Alliance Executive Officer (or designee) approval is required.

## **8.0 DOSAGE MODIFICATION BASED ON ADVERSE EVENTS**

The study medication dose should be stopped for any grade 3 or worse toxicities related to study agent, or at the patient's discretion regarding toxicity. Any of the above should be clearly recorded on the Adverse Event Form.

Patients can be discontinued abruptly (no need to taper).

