## **10.0 ADVERSE EVENT (AE) REPORTING AND MONITORING**

The prompt reporting of adverse events is the responsibility of each investigator engaged in clinical research, as required by Federal Regulations. Adverse events must be described and graded using the terminology and grading categories defined in the NCI's Common Terminology Criteria for Adverse Events (CTCAE), Version 4.0. However, CTCAE v5.0 must be used for serious AE reporting through CTEP-AERS as of April 1, 2018. The CTCAE is available at [REDACTED]. Attribution to protocol treatment for each adverse event must be determined by the investigator and reported on the required forms, using the codes provided.

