**15.1.7 Known potential toxicities**

The use of armodafinil is contraindicated in patients with hypersensitivity to armodafinil, modafinil, or any component of the formulation.

Use is not recommended in patients with a history of angina, cardiac ischemia, recent history of MI, left ventricular hypertrophy, or patients with mitral valve prolapse, who have developed mitral valve prolapse syndrome with previous CNS stimulant use.

Angioedema and hypersensitivity (with rash, dysphagia, and bronchospasm) have been observed with armodafinil. Small average increases in mean systolic and diastolic blood pressure were seen in patients with narcolepsy taking armodafinil when compared to placebo.

Serious and life-threatening rashes including Stevens-Johnson syndrome, toxic epidermal necrolysis, and drug rash with eosinophilia and systemic symptoms have been reported with modafinil, the racemate of armodafinil. Most cases have been reported within the first 5 weeks of therapy.

In pre-approval narcolepsy, OSA and SWD controlled trials of armodafinil, anxiety, agitation, nervousness, irritability, and depression were reasons for treatment

discontinuation more often than for placebo. Cases of suicide ideation were also observed in clinical trials.

The use of armodafinil may impair the ability to engage in potentially hazardous activities.

The agent should be administered at a reduced dose for patients with severe hepatic impairment. There is inadequate information to determine the safety and efficacy of dosing patients with severe renal impairment. Elimination of the agent and its metabolites may be reduced in elderly patients. Consideration should be given to the use of lower doses in this population.

Headaches are dose related and reported in > 10% of patients. Adverse reactions reported in 4 to 10% of patients include nausea (dose related), dizziness, insomnia (dose related), anxiety, and diarrhea. Adverse events reported in < 4% of patients include: depression (dose related), dyspepsia, fatigue, palpitations, rash (dose related), upper abdominal pain, agitation, anorexia, constipation, contact dermatitis, decreased appetite, depressed mood, attention disturbance, dyspnea hyperhidrosis, increased heart rate, flu-like syndrome, loose stools, migraine, nervousness, pain, paresthesia, polyuria, pyrexia, thirst, tremor, xerostomia (dose related), and vomiting.

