#### **15.1.9 Nursing Guidelines**

- Patients must take drug in the morning, with or without breakfast.
- Headaches are possibility. Instruct patients to contact study staff if they develop new onset of headaches.
- Instruct patient to monitor for hypersensitivity reactions such as rash and itching. Patients should immediately report any signs of fever, spreading rash, or joint aches.

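### Section 8.0 requires no stop for a suspected grade 1-2 hypersensitivity reaction, although section 15.1.7 contraindicates armodafinil in hypersensitivity without a grade limit

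*Combined protocol and SAP*

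**What the plan says.** Section 8.0 has two triggers for stopping: "The study medication dose should be stopped for any grade 3 or worse toxicities related to study agent, or at the patient's discretion regarding toxicity." It adds that the drug can be stopped abruptly. It has no trigger specific to hypersensitivity, rash or angioedema, and none that rests on the investigator's discretion.

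Section 15.1.7 describes the hazard:

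- "The use of armodafinil is contraindicated in patients with hypersensitivity to armodafinil, modafinil, or any component of the formulation."
- "Angioedema and hypersensitivity (with rash, dysphagia, and bronchospasm) have been observed with armodafinil."
- On the racemic parent drug: "Serious and life-threatening rashes including Stevens-Johnson syndrome, toxic epidermal necrolysis, and drug rash with eosinophilia and systemic symptoms have been reported with modafinil." On timing: "Most cases have been reported within the first 5 weeks of therapy."

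Section 15.1.9 covers detection: "Instruct patient to monitor for hypersensitivity reactions such as rash and itching." It continues: "Patients should immediately report any signs of fever, spreading rash, or joint aches." It states no action on study drug.

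Section 10.0 places causality with the site: "Attribution to protocol treatment for each adverse event must be determined by the investigator." Under section 13.0, a patient who stops the agent before 8 weeks goes off study.

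**The concern.** A severity grade is a reasonable stopping threshold for most side effects of a stimulant, such as headache, nausea or insomnia. It suits hypersensitivity less well, because there the question is whether the patient is reacting to the drug at all, and section 15.1.7 words its contraindication in that way. A site that receives a call about a spreading rash with low fever finds the reporting instruction in 15.1.9, and then a written stopping rule that depends on grade 3 or on the patient's own choice.

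What is at stake is patient safety. A patient with an early reaction could continue a drug linked to angioedema and, through its racemate, to life-threatening rash. The 8-week course contains the whole 5-week window in which most of the serious modafinil rashes were reported. Across many sites, the decision should not depend on who takes the call.

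**Working it through.** **Comparing the sections.** Take a patient with a reaction that the investigator suspects is hypersensitivity and grades 1 or 2.

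| Section | What it covers | Requires a stop here? |
|---|---|---|
| 3.2.2 | Excludes a history of hypersensitivity to other psychostimulants | No; entry only |
| 7.2 | Stop if treatment is unblinded | No |
| 8.0 | Related toxicity of grade 3 or worse, or patient's discretion | Only if the patient chooses |
| 9.0 | Off study if another fatigue treatment is started | No |
| 13.0 | What follows once the agent is discontinued | No |
| 15.1.7 | Contraindication, no grade limit | Not written as a stopping rule |
| 15.1.9 | Monitor and report signs | No action on drug stated |
| 16.6 | Suspends accrual on grade 4 or higher events | No; trial level |

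No row gives a required stop. The gap is in the grade threshold only, since relatedness is already the investigator's judgment under 10.0.

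**Exposure.** Two of three arms receive armodafinil: 330 × 2/3 = 220 patients. This counts everyone on active drug; it does not estimate how many would react.

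**Cost of adding a rule (illustration).** Section 16.2 plans 100 patients per arm, 10% versus 25% response, and a two-sided Fisher's exact test at 5%, and states 80% power. Summing the rejection probability over both binomial distributions gives 76.2%. That shortfall is a separate matter; 76.2% is the base here.

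Assumptions: a patient who stops early stays evaluable under 16.3 and counts as a non-responder. Section 16.3 does not say how such patients are counted, and 16.8 lists several ways of handling missing data without naming a main one. With a fraction s stopping, the response rate becomes rate × (1 − s).

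| Stop fraction | Armodafinil | Placebo | Power | Loss (points) |
|---|---|---|---|---|
| 0 | 25% | 10% | 76.2% | – |
| 1%, armodafinil only | 25% × 0.99 = 24.75% | 10% | 74.9% | 1.3 |
| 1%, both arms | 24.75% | 10% × 0.99 = 9.9% | 75.7% | 0.5 |
| 4%, armodafinil only | 25% × 0.96 = 24.0% | 10% | 70.8% | 5.4 |
| 4%, both arms | 24.0% | 10% × 0.96 = 9.6% | 74.0% | 2.2 |

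The 1% is an assumption. The 4% is the ceiling of the band in which 15.1.7 lists rash, so it prices a broader rule that stops every patient with a rash. Neither is a bound: hypersensitivity without rash has no stated rate, and the band is not specific to glioma patients. The table also assumes that none of these patients would have stopped under the current text, which tends to overstate the added cost.

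**The case against.** The strongest reply is that the protocol already gives the answer. An investigator who concludes that a patient has become hypersensitive reads in 15.1.7 that the drug is contraindicated. Section 8.0 says when drug must stop; it does not direct anyone to continue below grade 3. Patients may stop for toxicity of any grade, no taper is needed, 15.1.9 brings the signs to staff, and the Appendix XII calls at weeks 4 and 8 are partly there to deal with problems. Most of this stands. A reader might infer that 8.0 contradicts 15.1.7 or obliges a site to keep dosing; the text supports neither. What remains is that the only written stopping rule uses a threshold that does not fit a hazard the same protocol names. Applying the contraindication to a suspected reaction on treatment is a clinical inference that 8.0 leaves the site to make.

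A second reply is that angioedema, bronchospasm and the severe skin reactions may always grade 3 or worse, in which case 8.0 already stops the drug. The CTCAE definitions were not available, so this cannot be settled here. The point therefore should not be read as saying that patients with those events stay on drug. It concerns the earlier or milder presentation.

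A third reply is that a stop for any possibly related rash would be too broad. That is correct. Section 15.1.7 lists rash and contact dermatitis among ordinary events in under 4% of patients, concurrent chemotherapy is allowed, and every stop takes the patient off study. A reader might infer that every mild rash calls for permanent discontinuation; the documents do not support that.

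**Conclusion.** The point holds as a mismatch between sections. In the supplied text, a suspected grade 1-2 hypersensitivity reaction triggers no required stop, while the contraindication carries no grade limit and the reporting instruction leads to no stated action. The amendment is worth making because the hazard is foreseeable and can be severe and the edit is small.

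The size of the harm cannot be given, because the documents contain no hypersensitivity rate and no rate at which mild reactions progress. The finding covers the supplied text only: the consent and patient-information pages and the package insert, to which section 10.3.1 refers, could carry a stop instruction.

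**What to change.** Add to section 8.0: *Study drug should also be stopped, at any grade, for a suspected hypersensitivity reaction to study agent in the investigator's judgment (for example angioedema, bronchospasm, or rash that is spreading or accompanied by fever or joint aches).* Cross-refer section 15.1.9 to this sentence. Leave an isolated mild rash to the investigator. A rash and itching prompt in the Appendix XII call guide is optional; it would help mainly at week 4, since the 56-tablet supply is ending by week 8.

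The cost is one sentence and one cross-reference. The rule applies alike in all blinded arms, so a few more patients, some on placebo, would stop early and go off study. At the assumed 1% the power loss is the 0.5 to 1.3 points worked out above; the larger losses at 4% belong to the broader rash rule, which is not recommended.

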## **9.0 ANCILLARY TREATMENT/SUPPORTIVE CARE**

Patients who begin using any other pharmacologic agents or nonpharmacologic interventions after registration to specifically treat fatigue including psychostimulants, antidepressants, acupuncture, etc. will be taken off study.

**Note:** Antidepressants used to treat items other than fatigue (such as hot flashes or depression) are allowed if the patient has been on a stable dose for  $\geq$  28 days and plans to continue for the duration of the trial. Erythropoietin agents to treat anemia are allowed.

## **10.0 ADVERSE EVENT (AE) REPORTING AND MONITORING**

The prompt reporting of adverse events is the responsibility of each investigator engaged in clinical research, as required by Federal Regulations. Adverse events must be described and graded using the terminology and grading categories defined in the NCI's Common Terminology Criteria for Adverse Events (CTCAE), Version 4.0. However, CTCAE v5.0 must be used for serious AE reporting through CTEP-AERS as of April 1, 2018. The CTCAE is available at [REDACTED]. Attribution to protocol treatment for each adverse event must be determined by the investigator and reported on the required forms, using the codes provided.

### **10.1 Routine Adverse Event Reporting**

Adverse event data collection and reporting, which are required as part of every clinical trial are done to ensure the safety of patients enrolled in the studies as well as those who will enroll in future studies using similar agents. Adverse events are reported in a routine manner at scheduled times according to the test schedule in Section 4.0. For this trial, the Adverse Events forms are used for routine AE reporting (see Section 18.2 for adverse event form submission details).

## 10.2 CTCAE Routine Study Reporting Requirements

### \* Combinations of CTCAE Grade & Attribution Required for Routine AE Data Submission on Case Report Forms (CRFs)

Attribution	Grade 1	Grade 2	Grade 3	Grade 4	Grade 5
Unrelated			a	a	a
Unlikely			a	a	a
Possible		a	a, b	a, b	a, b
Probable		a	a, b	a, b	a, b
Definite		a	a, b	a, b	a, b

- a) Adverse Events: Other CRF - Applies to AEs occurring between registration and within 30 days of the patient's last treatment date, or as part of the Clinical Follow-Up Phase.
- b) Adverse Events: Late CRF - Applies to AEs occurring greater than 30 days after the patient's last treatment date.

## 10.3 Expedited adverse event reporting (CTEP-AERS)

Investigators are required by Federal Regulations to report serious adverse events as defined below. Alliance investigators are required to notify the Alliance Central Protocol Operations Program Office, the Study Chair, and their Institutional Review Board if a patient has an adverse event requiring expedited reporting. All such events must be reported in an expedited manner using the CTEP Adverse Event Reporting System (CTEP-AERS). In the rare occurrence when internet connectivity is lost, a 24-hour notification is to be made to the Alliance Central Protocol Operations Office. Once internet connectivity is restored, the 24-hour notification phoned in must be entered electronically into CTEP-AERS by the original submitter at the site.

**CTCAE term (AE description) and grade:** The descriptions and grading scales found in the revised NCI Common Terminology Criteria for Adverse Events (CTCAE) version 5.0 will be utilized for AE reporting beginning April 1, 2018. All appropriate treatment areas should have access to a copy of the CTCAE version 5.0. A copy of the CTCAE version 5.0 can be downloaded from the CTEP web site: [REDACTED] All reactions determined to be "reportable" in an expedited manner must be reported using the Cancer Therapy Evaluation Program Adverse Event Reporting System (CTEP-AERS).

The Alliance requires investigators to route all expedited adverse event reports through the Alliance Central Protocol Operations Program Office for Alliance coordinated studies.

Be sure to read this entire protocol section, as requirements are described in both the table and bullet points following the table. Note that the additional instructions or exclusions are protocol specific, and in the case of a conflict, the additional instructions or exclusions supersede the table.

**Note: All deaths on study require both routine and expedited reporting regardless of causality. Attribution to treatment or other cause should be provided.**

### 10.3.1 Alliance A221101 Reporting Requirements

Expedited reporting requirements for adverse events that occur on studies under an IND/IDE  $\leq$  30 Days of the last administration of the investigational agent/intervention 

#### FDA REPORTING REQUIREMENTS FOR SERIOUS ADVERSE EVENTS (21 CFR Part 312)

**NOTE:** Investigators **MUST** immediately report to the sponsor (NCI) **ANY** Serious Adverse Events, whether or not they are considered related to the investigational agent(s)/intervention (21 CFR 312.64)

An adverse event is considered serious if it results in **ANY** of the following outcomes:

- 1) Death
- 2) A life-threatening adverse event
- 3) An adverse event that results in inpatient hospitalization or prolongation of existing hospitalization for  $\geq$  24 hours
- 4) A persistent or significant incapacity or substantial disruption of the ability to conduct normal life functions
- 5) A congenital anomaly/birth defect.
- 6) Important Medical Events (IME) that may not result in death, be life threatening, or require hospitalization may be considered serious when, based upon medical judgment, they may jeopardize the patient or subject and may require medical or surgical intervention to prevent one of the outcomes listed in this definition. (FDA, 21 CFR 312.32; ICH E2A and ICH E6).

**ALL SERIOUS** adverse events that meet the above criteria **MUST** be immediately reported to the NCI via CTEP-AERS within the timeframes detailed in the table below.

Hospitalization	Grade 1 Timeframes	Grade 2 Timeframes	Grade 3 Timeframes	Grade 4 & 5 Timeframes
Resulting in Hospitalization $\geq$ 24 hrs	10 Calendar Days			24-Hour; 5 Calendar Days
Not resulting in Hospitalization $\geq$ 24 hrs	Not required		10 Calendar Days	

#### Expedited AE reporting timelines are defined as:

- o “24-Hour; 5 Calendar Days” - The AE must initially be reported via CTEP-AERS  $\leq$  24 hours of learning of the AE, followed by a complete expedited report  $\leq$  5 calendar days of the initial 24-hour report.
- o “10 Calendar Days” - A complete expedited report on the AE must be submitted  $\leq$  10 calendar days of learning of the AE.

 Serious adverse events that occur more than 30 days after the last administration of investigational agent/intervention and have an attribution of possible, probable, or definite require reporting as follows:

#### **Expedited 24-hour notification followed by complete report $\leq$ 5 calendar days for:**

- All Grade 4, and Grade 5 AEs

#### **Expedited 10 calendar day reports for:**

- Grade 2 adverse events resulting in hospitalization or prolongation of hospitalization
- Grade 3 adverse events

- Expedited AE reporting timelines defined:
  - ◆ “24 hours; 5 calendar days” – The investigator must initially report the AE via CTEP-AERS  $\leq$  24 hours of learning of the event followed by a complete CTEP-AERS report  $\leq$  5 calendar days of the initial 24-hour report.
  - ◆ “10 calendar days” - A complete CTEP-AERS report on the AE must be submitted  $\leq$  10 calendar days of the investigator learning of the event.
- Use the NCI protocol number and the protocol-specific patient ID provided during trial registration on all reports.

#### **Additional Instructions or Exclusions:**

- All adverse events reported via CTEP-AERS (i.e., serious adverse events) should also be forwarded to your local IRB.
- Grade 3/4 hematosuppression and hospitalization resulting from such do not require CTEP-AERS, but should be submitted as part of study results. All other grade 3, 4, or 5 adverse events that precipitate hospitalization or prolong an existing hospitalization must be reported via CTEP-AERS.
- Treatment expected adverse events include those listed in Section 15.0 and in the package insert
- Death due to progressive disease should be reported as Grade 5 “Disease progression” in the system organ class (SOC) “General disorders and administration site conditions.” Evidence that the death was a manifestation of underlying disease (e.g., radiological changes suggesting tumor growth or progression: clinical deterioration associated with a disease process) should be submitted.
- Any death occurring within 30 days of the last dose, regardless of attribution to the investigational agent/intervention requires expedited reporting within 24 hours.
- Any death occurring greater than 30 days after the last dose of the investigational agent/intervention requires expedited reporting within 24 hours only if it is possibly, probably, or definitely related to the investigational agent/intervention.
- All new malignancies must be reported through CTEP-AERS whether or not they are thought to be related to either previous or current treatment. All new malignancies should be reported, i.e., solid tumors (including non-melanoma skin malignancies), hematologic malignancies, myelodysplastic syndrome (MDS)/acute myelogenous leukemia (AML), and *in situ* tumors.

#### **Secondary Malignancy:**

A secondary malignancy is a cancer caused by treatment for a previous malignancy (e.g., treatment with investigational agent/intervention, radiation or chemotherapy). A secondary malignancy is not considered a metastasis of the initial neoplasm.

CTEP requires all secondary malignancies that occur following treatment with an agent under an NCI IND/IDE be reported via CTEP-AERS. Three options are available to describe the event:

- Leukemia secondary to oncology chemotherapy (e.g., acute myelocytic leukemia [AML])
- Myelodysplastic syndrome (MDS)
- Treatment-related secondary malignancy

Any malignancy possibly related to cancer treatment (including AML/MDS) should also be reported via the routine reporting mechanisms outlined in each protocol.

